4.4 Rationale for the Current Study

DMD is a rare, serious, debilitating, and ultimately fatal, disease for which there is an urgent need to develop safe and effective therapies. In order to efficiently meet this urgency and the needs of the subject community, the study evaluates the efficacy and safety of casimersen, eteplirsen, and of golodirsen administration over approximately 1 year in DMD subjects with duplication mutations amenable to treatment by exon 45, 51 or exon 53 skipping. Skipping of a single copy of the duplicated exon is expected to result in a wild-type (WT) *DMD* transcript allowing the expression of a WT, full length dystrophin protein. Successful skipping of a single copy of the duplicated exon in *in vitro* and *in vivo* models has been reported in the literature²⁷⁻²⁹. Casimersen, eteplirsen, and golodirsen have the potential to be disease-modifying treatments for boys with DMD mutations amenable to exon 45, 51 and exon 53 skipping, respectively.

As summarized in Section 4.3 and in the casimersen and golodirsen Investigator's Brochures, the totality of the non-clinical data with these PMOs as well as AVI-4225 (targeting exon 23) and eteplirsen suggests that PMOs are well tolerated in the non-clinical setting. Moreover, treatment with eteplirsen (at 30 mg/kg and 50 mg/kg) has been well-tolerated by boys with DMD deletion mutations amenable to skipping exon 51.

The relatively low expected risk for subjects exposed to casimersen, eteplirsen, or golodirsen and the urgent medical need for a treatment for this subject population support the conclusion that the potential benefits of exposing subjects to casimersen, eteplirsen, or golodirsen outweigh the potential risks.

5 STUDY OBJECTIVES

5.1 Primary Objective

Primary objective are to evaluate the effect of either casimersen, eteplirsen, or golodirsen on:

- To evaluate the efficacy of casimersen (previously SRP-4045), eteplirsen (previously AVI-4658), or golodirsen (previously SRP-4053) on dystrophin expression as assessed by quantification of protein in muscle biopsy tissue by western blot.
- Safety and tolerability in a population of subjects with relevant exon duplications using the following outcome measures:
 - Adverse events (AEs), serious adverse events (SAEs), deaths, and discontinuations due to AEs
 - Laboratory testing may include the following (See Section 9 for details):
 - Hematology
 - Coagulation
 - Chemistry
 - Urinalysis
 - Cardiac function including ECG and ECHO
 - Vital signs
 - Physical examination findings

5.2 Secondary Objectives

Secondary objectives of this study is to evaluate the effect of either casimersen, eteplirsen, or golodirsen after 48 weeks of treatment on:

- Expression of dystrophin as measured by immunofluorescent signal intensity and percent dystrophin positive fibers (PDPF) in muscle tissue sections in comparison to baseline values.
- The efficiency of splicing alteration will be measured by RNA Sequencing (RNA-Seq) to establish *DMD* mRNA copy number and the exon-exon junction frequency quantified, with normalization to exon junction read values from an exon junction in regions distinct from the targeted exon.

5.3 Exploratory Objectives

Additional objectives are to evaluate the effect of casimersen, eteplirsen, or golodirsen analysing the changes from baseline to week 48 in the following:

- Functional abilities of subjects in comparison to the expected natural history using the following measures:
 - Subjects between 6 to 36 months of age at enrollment: Bayley Scales of Infant Development - Gross motor functions and fine motor functions.
 - Motor function as measured on the North Star Ambulatory Assessment (NSAA, ambulant boys age 3 years and older).
 - Ambulant subjects over age 3.5 years: endurance and muscle function as measured by the 100-Meter Walk / Run Test (100M)
 - ACTIVE-seated for boys over 5 years of age.
 - Forced vital capacity, as measured in absolute values and by % predicted forced vital capacity (FVC%) in patients aged ≥ 10 years
 - Peak expiratory flow as reported as % predicted by age and height (%PEF)
 - Timed functional tests for ambulant subjects 3 years or older:
 - time to complete 10-meter run
 - time to rise from the floor
 - time to climb 4 steps
 - time to descend 4 steps
- Pediatric Outcomes Data Collection Instrument (PODCI) for patients ages 2-17.
- Adult Patient-Reported Outcomes Measurement Information System (PROMIS) Upper Extremity Report for patients 18+ years.
- Immune staining may be performed on biopsy specimens for members of the dystrophin-associated protein complex, such as the sarcoglycans, dystroglycans and n-Nos.
- Muscle morphometrics may also be performed, including fiber size histograms and quantification of central nucleation.

6 INVESTIGATIONAL PLAN

6.1 Overall Study Design

This is a open label, 48-week study to evaluate the efficacy and safety of three PMOs – casimersen, eteplirsen, and golodirsen – in 6 subjects with genotypically confirmed *DMD* with duplication mutations amenable to correction by skipping exon 45, 51, and 53, respectively.

Subjects will be evaluated for inclusion during a Screening period of approximately 8 weeks. Eligible subjects who have out-of-frame duplications of a single exon that may be corrected by skipping exon 45, 51, or 53 will receive once weekly intravenous (IV) infusions of 30 mg/kg casimersen, 30 mg/kg eteplirsen, or 30 mg/kg golodirsen respectively for 48 weeks.

Upon qualification for the study based on Screening and Baseline assessments, all subjects will undergo a muscle biopsy for baseline assessment of dystrophin expression. All subjects will undergo a second biopsy at 48 weeks of treatment.

Efficacy will be assessed at regularly scheduled (12 week intervals) study visits and safety will be monitored on an ongoing basis for all subjects.

Safety will be assessed through the collection of adverse events (AEs), laboratory tests, electrocardiograms (ECGs), echocardiograms (ECHOs), vital signs, and physical examinations throughout the study as described in the Schedule of Events (Table 6). A Safety Follow Up phone call will be placed approximately 4 weeks (28 days) after the last study infusion to check for new adverse events, to obtain any new information regarding ongoing AEs and/or any other noteworthy subject progress.

At the conclusion of the 48 week study period, subjects will be enrolled in the Sarepta Clinical Transition Program via the SareptAssist patient support program. Subjects will be followed clinically in the NCH DMD clinic for safety, specifically for monitoring of renal function as per the prescribing information for casimersen and golodirsen. All prescribing recommended testing will be performed for clinical monitoring only. Those subjects receiving golodirsen or casimersen via this program will be monitored by urine dipstick every month, and serum cystatin C and urine protein to creatinine ratio (UPCR) every three months. There is no additional clinical safety testing recommended per the prescribing information for eteplirsen.

Additionally, through this program the subjects will be provided uninterrupted weekly drug access after conclusion of the 48 week study period. Subjects will remain on the Clinical TransitionProgram/SareptAssist until study samples can be analyzed and insurance authorization for the drug(s) can be obtained, or the efficacy of the drug is determined to not meet the standards for continuation. The threshold for study drug continuation in Sarepta's Clinical TransitionProgram/SareptAssist is a 10 percent increase in dystrophin positive fibers (defined as fibers with 30 percent of the circumference positive for dystrophin) as determined by immunofluorescence staining of the baseline and 48-week post-treatment muscle biopsies. Subjects will receive weekly drug infusions via home health care arranged by Sarepta Therapeutics and as noted above will be monitored clinically in the NCH DMD clinic.

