Post-treatment Follow-up/Clinical Transition Period	
Subjects will be followed up with by phone call approximately 4 weeks (28 days) following last infusion to check for adverse events or other significant findings.
 
At the conclusion of the 48 week study period, subjects will be enrolled in the Sarepta Clinical Transition Program and will be followed clinically in the NCH DMD clinic for safety, specifically for monitoring of renal function as per the prescribing information for casimersen and golodirsen. All prescribing recommended testing will be performed for clinically monitoring only. Those subjects receiving golodirsen or casimersen via this program will be monitored by urine dipstick every month, and serum cystatin C and urine protein to creatinine ratio (UPCR) every 3 months. There is no additional clinical safety testing recommended per the prescribing information for eteplirsen.- Additionally, through this program the subjects will be provided uninterrupted weekly drug access after conclusion of the 48 week study period. Subjects will remain on the Clinical Transition Program/SareptaAssist until study samples can be analyzed and insurance authorization for the drug(s) can be obtained, or the efficacy of the drug is determined to not meet the standards for continuation. The threshold for study drug continuation in Sarepta's Clinical Transition Program/SareptaAssist is a 10 percent increase in dystrophin positive fibers (defined as fibers with 30 percent of the circumference positive for dystrophin) as determined by immunofluorescence staining of the baseline and 48-week post-treatment muscle biopsies. Subjects will receive weekly drug infusions via home health care arranged by Sarepta Therapeutics and as noted above will be monitored clinically in the NCH DMD clinic.

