9 STUDY VISITS

The schedule outlining the study assessments and times of assessments is shown in Section 9.9 and all procedures are described in detail in Section 10. **All assessments scheduled on the same day as study treatment administration are to be completed prior to initiation of study treatment infusion.**

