9.1.3 Baseline

The baseline visit should occur 3-5 weeks after screening is completed and will occur over two days.

9.1.3.1 Day 1

The following assessments will occur at this visit:

- **Confirmation of eligibility**
- Medical history
- Adverse Events
- Concomitant Medications
- Full Physical Exam
- Vital Signs
- Height
- Weight
- ECG
- Bayley scale of Infant Development (6 to 36 months of age)
- 100M – ambulant subjects (3.5 years until non-ambulant)
- NSAA (3 years to non-ambulant)
- Active-seated – non ambulant subjects (5 years and older)
- Pulmonary functional test (PFT) (10 years and older)
- Timed functional tests for (ambulant subjects 3 years and older)
- Pediatric Outcomes Data Collection Instruments (PODCI, ages 2-17)
- Patient-Reported Outcomes Measurement Information System (PROMIS) Upper Extremity

Report (ages 18+)

The following blood lab work will occur at this visit:

- Complete Metabolic Panel (CMP)
- Amylase
- Gamma-glutamyl transpeptidase (GGT)
- Complete Blood Count (CBC)/Differential
- Coagulation Measures
- Uric Acid
- Lactate dehydrogenase (LDH)
- C-reactive Protein (CRP)
- Creatine Kinase (CK)
- Cystatin C

The following urine lab work will occur at this visit:

- Urinalysis

9.1.3.2 Day 2

A baseline open muscle biopsy will be performed in one gastrocnemius muscle or alternate muscle. (Note that the rationale and methods of muscle biopsy site selection and performance for this and subsequent biopsies are discussed in Section 10.2.1). If in the discretion of the principal investigator, an implanted venous access port needs to be placed prior to infusion, this placement may occur at the same time as the muscle biopsy. RNAseq analysis will be completed on tissue from this muscle biopsy.

If in the opinion of the Principal Investigator, a PORT placement is indicated, all attempts will be made to have this occur during this same sedation event (see Section 8.2 for full details), but if it is not feasible, a separate visit will be scheduled to place the port.

9.2 Week 1

Week 1 should occur within 4 weeks of the Baseline Functional Assessment Visit. If the Week 1 visit is > 4 weeks after Baseline, the subject is required to repeat the Baseline functional assessments to reconfirm eligibility.

Infusion with the study drug will begin at Week 1 and will occur weekly through the week 48 visit. For details regarding the infusion, please see Section 8.2.

The following assessments will occur at this visit:

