9.6 Weeks 16, 20, 28, 32, 40 and 44 (+/- 1 week)

The following assessments will occur at this visit:

- Medical history
- Adverse Events
- Concomitant Medications
- Brief Physical Exam
- Vital Signs
- Weight
- Infusion

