10.1.2 Clinical Laboratory Evaluations

The following routine clinical laboratory tests will be performed at the time points specified in Section 9. Safety samples will be collected analyzed by an accredited central laboratory:

Hematology:	White blood cells (WBC), hemoglobin, hematocrit, platelets, red blood cells (RBCs), neutrophils, lymphocytes, monocytes, eosinophils, basophils, and any abnormal cells
Coagulation:	Prothrombin time, international normalized ratio (INR), and activated partial thromboplastin time (aPTT)
Chemistry:	Complete Metabolic Panel [CMP, including: sodium, potassium, chloride, carbon dioxide, blood urea nitrogen (BUN), creatinine, glucose, calcium, total protein, albumin, total bilirubin, alanine aminotransferase (ALT), aspartate aminotransferase (AST), and alkaline phosphatase], amylase, gamma-glutamyl transferase (GGT), uric acid, lactate dehydrogenase (LDH), C-reactive protein (CRP), creatine kinase (CK), and serum cystatin C
Immunology:	Hepatitis B, C and HIV
Urine:	Urinalysis (including: specific gravity, pH, cytology, hemoglobin, protein, glucose, and ketones)

** For subjects taking drugs that potentially induce GGT synthesis through the cytochrome P450 system, the clinically significant range will be estimated at two times the levels obtained from the baseline screening test.*

Any value outside of the current reference ranges for the laboratory performing the test will be flagged on the laboratory results. The Investigator will determine whether abnormal assessment results are clinically significant (CS) or not clinically significant (NCS). Clinical significance is defined as any variation in assessment results that has medical relevance resulting in an alteration in medical care. If clinically significant deterioration from Baseline levels is noted, the Investigator will continue to monitor the subject with additional assessments until:

- Values have reached normal range and/or Baseline levels

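### For casimersen and golodirsen, in-trial urine testing after Week 12 is sparser than the renal schedule the protocol cites for use after the study, and no UPCR is planned

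*Combined protocol and SAP*

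**What the plan says.** Section 6.1 and the synopsis describe what happens once the 48 weeks are over. Subjects move to a transition programme, continue weekly infusions, and are followed for renal function in line with the casimersen and golodirsen labels. Subjects on either drug "will be monitored by urine dipstick every month, and serum cystatin C and urine protein to creatinine ratio (UPCR) every three months". Section 6.1 adds: "All prescribing recommended testing will be performed for clinical monitoring only". For the third drug it says: "There is no additional clinical safety testing recommended per the prescribing information for eteplirsen".

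For the trial itself, Section 9.2 states: "Infusion with the study drug will begin at Week 1 and will occur weekly through the week 48 visit". Sections 9.1 to 9.8 and Table 6 place urinalysis at Screening, Baseline and Weeks 1, 4, 8, 12, 24, 36 and 48. Section 10.1.2 counts protein among its components. Cystatin C, creatinine and BUN are drawn at those same visits. Section 9.6, which covers Weeks 16, 20, 28, 32, 40 and 44, lists no blood or urine test. UPCR does not appear in Section 9, Table 6 or 10.1.2.

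Section 6.2 identifies the kidney as the principal target organ in the animal studies. It regards 30 mg/kg of casimersen or golodirsen as safe on the ground that this organ can be monitored clinically.

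**The concern.** Safety is a primary objective, and the dose rationale for two of the three drugs depends on watching the kidney. Yet the protocol sets out a renal schedule, attributes it to those drugs' labels, and starts it only when the subject has left the trial. The drugs and the weekly dosing are the same before and after that point, so urine is checked more often once the study is over than during most of it. The protocol gives no reason.

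What is at stake is proteinuria without symptoms. If it begins between two samples, weekly adverse event review and vital signs will not show it. The blood markers do not fill the gap either, because they are drawn at the same visits as the urine. With no UPCR at Baseline, the first scheduled ratio would come after 48 weeks of dosing, with no pre-treatment value to compare it with.

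**Working it through.** The plan states no figure to reproduce; the check is a count from the schedule.

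**Inputs**
- Urinalysis: Screening, Baseline, Weeks 1, 4, 8, 12, 24, 36, 48 (9.1 to 9.8, Table 6) = 9 rounds, 7 of them from Week 1 on. The Week 1 sample comes before the first dose, so 6 follow dosing.
- Doses: weekly, Weeks 1 to 48 = 48 (9.2).
- Order on the day (Section 9): "All assessments scheduled on the same day as study treatment administration are to be completed prior to initiation of study treatment infusion".
- Window: +/- 1 week at each visit from Week 4 (9.3 to 9.8).
- Benchmark: monthly dipstick; cystatin C and UPCR every three months (6.1). A month is 52/12 = 4.33 weeks, so the existing four-weekly visits are the nearest match. Three months is 52/4 = 13 weeks.

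**Slots after Week 12**
- Four-weekly slots: 16, 20, 24, 28, 32, 36, 40, 44, 48 = 9.
- With a urine test: 24, 36, 48 = 3. Without: 9 - 3 = 6.
- On calendar months the result is similar: 36/4.33 = 8.3 tests would be expected, against 3 scheduled.
- Up to Week 12 the intervals are 3, 4 and 4 weeks, so there is no shortfall there.

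**Gaps and doses between samples**
- Nominal gap: 24 - 12 = 12 weeks, and the same for 24 to 36 and 36 to 48.
- Samples precede the infusion, so the doses between the Week 12 and Week 24 samples are those of Weeks 12 to 23 = 12. Four-weekly testing would give 4.
- Over the three intervals: Weeks 12 to 47 = 36 doses, and 36/48 = 75% of all doses.
- With windows: one visit a week early and the next a week late gives 12 + 2 = 14 weeks. A four-weekly schedule would stretch likewise to 4 + 2 = 6 weeks.

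**Delay to the next scheduled sample**
Assume proteinuria that persists once it starts, with onset uniform within an interval of length L. Mean delay is L/2.
- As scheduled: 12/2 = 6 weeks; longest 12 nominally, 14 with windows.
- Four-weekly: 4/2 = 2 weeks; longest 4 nominally, 6 with windows.

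**Cystatin C**
The longest nominal gap is 12 weeks, against 13. The interval is met nominally, though a 14-week gap at the window limits would exceed it by one week.

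**UPCR**
Scheduled in the trial: 0. A baseline and 12-weekly tests would give 1 + 4 = 5.

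**Subjects**
Six are planned and assigned by genotype (7.1), with no number per drug. The affected number is 0 to 6.

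**The case against.** The strongest reply is that the cited schedule belongs to a different setting. It is written for subjects infused at home after the study and is described there as clinical monitoring only. In the trial, subjects are seen weekly, observed for an hour after each infusion, and have nine rounds of urinalysis with cystatin C, creatinine and BUN. Significant renal illness and aminoglycoside use are grounds for exclusion (7.3), clinically significant results trigger follow-up (10.1.2), and the DSMB receives a summary of them (13.4). Section 6.2 sets no monitoring interval. It also reports no adverse effect in mice at 960 mg/kg (casimersen) and 120 mg/kg (golodirsen). The labels cannot be read here, and the Investigator's Brochures, also not available, may support the sparser schedule.

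Much of this stands. A reader might infer that the protocol breaks its own rule or departs from the labels. The documents do not support that: the schedule is stated for the period after the study, and all that can be tested is the protocol's own account of the labels. The safeguards are real, but none detects silent proteinuria between samples. Weekly review relies on symptoms and signs, the blood markers share the urine visits, and the follow-up rule and DSMB summary begin only after an abnormal result.

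A second objection is that more testing brings no stated action. This also stands in part. Section 8.2.1 makes no allowance for changing the dose, and the proposed fix sets no numeric threshold, so any benefit runs through the Investigator's judgement under 10.1.2.

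**Conclusion.** The point holds as a gap in safety monitoring for casimersen and golodirsen subjects. After Week 12, 6 of 9 four-weekly slots lack a urine test, the gap between tests is 12 weeks nominally and up to 14 within the windows, and no UPCR is planned at any time. The trial relies on kidney monitoring to justify the dose, yet tests urine less often than the schedule the protocol cites for the same drugs.

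The mean delay of 6 weeks against 2 rests on assumed uniform onset and persistence, and no event rate is available to turn it into expected cases. If every enrolled subject has an exon 51 duplication, nobody is affected.

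Two stronger readings should be avoided. Because Section 6.2 mentions animal kidney findings after 12 weeks of dosing and urine testing thins at Week 12, a reader might infer that the sparse period is the period of risk. Section 6.2 gives a dosing duration, not a time of onset. Nor can it be said that proteinuria goes unmonitored: urine protein is tested throughout, only less often and without a ratio. The change is advisable because it is cheap, not because harm has been shown.

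**What to change.** For subjects on casimersen or golodirsen:

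1. Add a urine dipstick at Weeks 16, 20, 28, 32, 40 and 44 (9.6, Table 6).
2. Add UPCR at Baseline and Weeks 12, 24, 36 and 48, on urine already collected (Section 9, 10.1.2, Table 6).
3. When the Investigator judges a dipstick protein result clinically significant, use UPCR as the follow-up assessment under 10.1.2.
4. In 14.3.2.2, and where adverse events are tabulated by drug, note that urine testing was more frequent for these two drugs. Base any by-drug comparison of urinalysis on the weeks common to all three.

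Cystatin C needs no change, and eteplirsen subjects keep the present schedule.

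The cost is a protocol amendment and 6 + 5 = 11 scheduled urine tests per affected subject, so 0 to 66 in all, plus any follow-up UPCR. Only the dipsticks need a new collection: 6 per subject, 0 to 36 in all, at visits already planned. No blood draw or visit is added. There are two downsides. Collecting urine from infants may be awkward, since eligibility starts above 6 months of age. From Week 1 on, the two drugs would have 7 + 6 = 13 urine tests against 7 for eteplirsen, so urinary findings could be picked up more often for them; item 4 is there for that reason.

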6.2 Dose Selection Rationale

A dose of 30 mg/kg casimersen, eteplirsen, or golodirsen was selected to use in this study. Doses were chosen based on results from animal and phase 1 clinical studies with casimersen and golodirsen and on additional clinical data from eteplirsen. There are three ongoing clinical studies with golodirsen and casimersen in DMD patients (Study 4053-101, Study 4045-101 and Study 4045-301)²⁴⁻²⁶.

As described in Section 4.3, clinical studies 4658-us-201¹⁷ and 4658-us-202¹⁸ with eteplirsen assessed the efficacy, safety, and tolerability of eteplirsen (50 mg/kg and 30 mg/kg) administered as IV infusions in twelve 7- to 13-year old pediatric subjects diagnosed with DMD with out of frame mutations amenable to treatment by skipping exon 51.

At Week 48, the increases in the percent of dystrophin-positive fibers were similar for subjects who had received weekly 30 mg/kg and 50 mg/kg eteplirsen without interruption from Week 1 (52% and 42% of normal respectively, or 47% for the combined groups). These data suggest that the effect of eteplirsen on the production of novel dystrophin is not significantly different between the two doses tested in this

study. Thus, the lower dose of eteplirsen (30 mg/kg) was selected for further clinical study, as it is a more conservative choice given that subjects would receive eteplirsen as a life-long treatment.

Like eteplirsen, the PMOs casimersen and golodirsen have been evaluated in non-clinical studies to assess their pharmacological activity, pharmacokinetic, safety, and toxicology/toxicokinetic proprieties. RT-PCR studies using cultured muscle cells and demonstrated strong exon 45 (casimersen) and exon 53 (golodirsen) skipping activities. Both casimersen and golodirsen have shown low protein binding activity and low potential for drug-drug interactions, since they did not interact with cytochrome P450 isoenzymes at biologically relevant concentrations *in vitro*.

The non-clinical safety profiles of casimersen and golodirsen are similar to other PMOs tested to date; no cardiovascular, respiratory or central nervous system effects, genotoxicity, male reproductive toxicity, or immunotoxicity have been detected. The kidneys were the main target organ in mice and monkeys after 12 weeks of repeat dosing (weekly IV injections of casimersen and golodirsen) which is consistent with the renal excretion being the major elimination pathway for PMOs. No adverse effect were observed in mice using 960 mg/kg and 120 mg/kg of casimersen and golodirsen, and the maximum feasible dose for IV administration in monkeys was of 320 mg/kg for both PMOs. Because the potential target organ of toxicity (the kidney) can be monitored in the clinic, doses of 30 mg/kg casimersen or golodirsen are considered safe for once weekly IV infusions in DMD subjects with mutations amenable to exon 45 or exon 53 skipping. Additional non-clinical data for casimersen and golodirsen are described in the respective Investigator's Brochures.

Further, 30 mg/kg/wk golodirsen treatment in clinical trial 4053-101 resulted in a significant mean increase in dystrophin protein from baseline (N=25, p<0.001) at Week 48.

Due to the expected similarities among investigational PMOs for the treatment of subjects with DMD, a 30 mg/kg dose for eteplirsen, casimersen and golodirsen was selected for evaluation in this study.

